Clinical Trial Protocol				
Protocol Title	Testing of Identification Markers for strokE			
Acronym	TIME			
Version	2.0			
Version date	19th February 2021			
Study Sponsor	Pockit diagnostics Ltd, [name]			
Sponsor's Head of Clinical	[name], Pockit diagnostics Ltd			

Contents

1.	Abs	Abstract		
2.	Rationale		4	
3.	Aim	im of the study		
4.	Study endpoints		5	
4	1.1.	Primary outcomes	. 5	
2	1.2.	Secondary outcomes	. 5	
5.	Stu	dy design and methodology	5	
ŗ	5.1.	Patient recruitment	. 5	
Į	5.2.	Sample collection and processing	.6	
I	5.3.	Diagnostic criteria	.6	
Ĩ	5.4.	Biomarker measurement	.6	
6.	Stu	dy population	. 7	
Ċ	5.1.	Inclusion criteria	. 7	
Ċ	5.2.	Exclusion criteria	. 7	
ć	5.3.	Withdrawal criteria	. 7	
ć	5.4.	Sample size estimation	. 7	
7.	Dat	a management	8	
-	7.1. 7.1.1. 7.1.2.	Data sources and collected data Clinical data Biomarker data	. 8 .8 .8	
-	7.2.	Data management	. 9	
-	7.3.	Data storage	. 9	
	7.4. 7.4.1. 7.4.2. 7.4.3. 7.4.3. 7.4.4. 7.4.5. 7.4.6.	Data analysis plan Data exploration Whole blood biomarker concentrations Covariate analysis Biomarker kinetics Diagnostic performance Biomarker diagnostic thresholds	.9 10 10 10 10 10	
8	r.J. Refi	erences	12	
0.	i ci	Neielences		

1. Abstract

Rationale

Stroke is the third leading cause of death and the first cause of physical disability and dementia worldwide. Two main types of stroke exist, ischemic stroke (IS) and intracerebral haemorrhage (ICH), with similar symptoms, but different treatment. Among the population of ischemic strokes, large vessel occlusions (LVO) give rise to the most dangerous and deadly stroke subtype. A very effective treatment, called endovascular thrombectomy (EVT) is available for LVO patients, but it is only available at specialised centres around the country. Currently, there are no diagnostic methods able to identify LVO patients in the ambulance and direct them to EVT centres. Pockit diagnostics are developing a revolutionary innovation that combines highly specific blood biomarkers for LVO with stroke severity scales. The diagnostic algorithm identified by Pockit diagnostics has already shown 98% specificity and 95% accuracy for LVO detection. The TIME study will aid in the identification and evaluation of the diagnostic performance of the diagnostic algorithm designed by Pockit diagnostics.

Method

The TIME study is a multi-centre, observational prospective cohort study. Patients referred to the emergency department or stroke unit with a suspected stroke will be enrolled in the study. Up to 400 patients will be recruited and requested to provide one venous blood sample. Blood samples will be processed on site and frozen. Samples will be analysed retrospectively via standard laboratory assays.

Outcomes

The main outcome of the TIME study will be the validation of the clinical diagnostic performance of Pockit diagnostics' algorithm for LVO detection. This study will validate previously defined diagnostic thresholds for LVO identification.

2. Rationale

Stroke is among the leading causes of death and disability worldwide. Ischaemic stroke caused by large vessel occlusion (LVO) contributes disproportionally to these figures and accounts for 62% of post-stroke disabilities and 96% of post-stroke mortality¹.

Acute ischaemic stroke patients with LVO can be effectively treated with endovascular thrombectomy (EVT)², but this treatment is only available in comprehensive stroke centers (CSC) or other EVT-capable centers. Inter-hospital transfer of LVO patients from primary stroke centers to EVT-capable centers significantly delays time to treatment and leads to higher disability rates³. Identification of LVO patients in the pre-hospital setting (e.g. within an ambulance) could enable the transfer of LVO patients to EVT-capable centers directly, reducing time to treatment, functional disabilities, and deaths.

Multiple studies have investigated the ability of brief pre-hospital stroke assessment scales to identify LVO strokes in the field. Despite this, these severity scales lack the sensitivity and specificity required for triaging LVO patients with confidence, resulting in false negatives in patients with LVO and milder stroke as well as false positives in patients with stroke mimics or haemorrhagic strokes^{4,5}. A more accurate diagnostic test able to complement these assessment scores and direct LVO patients to EVT-capable centers is much needed.

Pockit diagnostics have ventured a novel strategy for the identification of LVO. By combining the measurement of D-dimer and GFAP with pre-hospital stroke severity scales (e.g. FAST-ED⁶), Pockit diagnostics have created a powerful diagnostic algorithm that has demonstrated accuracy of 95% (95%CI 87-99%) and specificity of 98% (95% CI 92-100%) for LVO detection⁷.

The aim of the TIME study is to validate the clinical diagnostic performance of previously defined diagnostic thresholds of Pockit diagnostics' algorithm. Results of this study will direct the development of a diagnostic test for identifying LVO patients in the field, directing them to EVT centre, ultimately enabling faster treatment, and improving patient outcomes.

3. Aim of the study

The primary aim of this study is to validate the clinical diagnostic performance of previously defined cut-off points on the plasma concentration of D-dimer and GFAP, combined with stroke severity scales (FAST-ED, FAST, EMSA, RACE, C-STAT).

The secondary aim of the study is to optimise the cut-off points of the diagnostic algorithm for LVO detection, in a larger and inter-racial patient population.

4. Study endpoints

4.1. Primary outcomes

Primary outcomes of the TIME study will be values of diagnostic accuracy, sensitivity, specificity, positive likelihood ratio (LR+) and negative likelihood ratio (LR-) of the model composed of D-dimer, GFAP and stroke severity scales (FAST-ED, FAST, EMSA, RACE, C-STAT) for identification of LVO.

4.2. Secondary outcomes

Secondary outcomes will be optimised values of ut-off points for the different diagnostic algoirthms (one per stroke severity scale evaluated) obtained in a larger interracial population.

5. Study design and methodology

The TIME study is designed as an observational prospective cohort study.

This study is designed to validate candidate biomarkers according to the STARD principles (http://www.equator-network.org/reporting-guidelines/stard/).

5.1. Patient recruitment

Patients will be recruited prospectively at their arrival to the emergency department (ED). Patients will be recruited as soon as possible after their arrival to ED and preferably before CT/MRI scans are performed. Patients recruitment will fit into standard clinical procedures for acute stroke management, with minimal disturbance to the patient.

The nurse or physician that is part of the team responsible for the patient's clinical care will identify potential subjects by initiating a "code stroke". Potential subjects will subsequently be provided with the patient information sheet. During the visit to the ED the local research assistant and/or physician will answer any remaining questions and inquire if patients are willing to contribute to the research project. If they wish to do so, informed consent will be obtained. All consent will be obtained by a qualified research assistant. Patients will always be given sufficient time to read the documentation and ask questions. Patients will be offered the possibility to take more time to consider participating. A legally authorized representative may also give consent for the patient's participation.

In case the patient is unconscious, or otherwise unable to provide informed consent, this will be considered as a specific circumstance and informed consent procedure may be waived (45 CFR 46.116). Venous blood is routinely withdrawn for standard clinical laboratory tests, and this research study does not involve additional risk for the patient. In addition, this study could not be carried out without the waiver, due to representation of unconscious patients in the target population. The population of LVO strokes is expected to be enriched

with patients presenting with more severe symptoms, including unconsciousness. Failure to recruit unconscious LVO patients, due to inability to obtain informed consent, can alter the representation of LVO patients in the final population. This could ultimately result in inappropriate statistical power and inability to observe optimal diagnostic performance. Importantly, identifiable private information of waived consent patients will not be made available to anyone outside the hospital site. If the patient regains consciousness during the stay at hospital site, informed consent will be obtained as per standard consent procedure for conscious patients.

5.2. Sample collection and processing

One 5 mL sample of venous blood will be collected from each consented patient. Blood will be collected using standard procedure. Briefly, blood samples from a single blood draw will be collected into tubes containing sodium EDTA and immediately placed on ice. Blood samples will be processed immediately or within 30 minutes from withdrawal. Blood samples collected into EDTA tubes will be centrifuged at 2000 g for 15 minutes at 4°C. Plasma will be divided into 3 aliquots of ~1 mL each and all plasma aliquots will be frozen at -80° C. Plasma aliquots will be stored at hospital site until transfer to Pockit diagnostics.

5.3. Diagnostic criteria

Patients admitted to the ED with suspected stroke will be recruited in the study. Patient population is expected to be composed of ~50% ischemic strokes (of which ~30-40% could have LVOs), ~40% stroke mimics, and ~10% haemorrhagic strokes.

Final diagnosis of stroke subtype or stroke mimics will be established based on CTbased and MRI-based neurologist report. Diagnosis of ischemic stroke will be based on a positive result from MRI scan. Diagnosis of LVOs will be based on results interpretation from CT angiography. Diagnosis of haemorrhagic stroke (ICH or subarachnoid haemorrhage) will be based on positive results from CT scan and, where possible, MRI scan too. Diagnosis of stroke mimics will be based on negative results from both CT scan and MRI scan. Final diagnosis of stroke mimics (i.e. migraine, encephalitis, epilepsy, etc) will be obtained from patient data, where possible. All diagnostic results will require interpretation from a qualified stroke neurologist.

5.4. Biomarker measurement

Upon transfer of plasma aliquots from hospital site to Pockit diagnostics, a panel of plasma proteins and metabolites will be measured by Pockit diagnostics. Measurement of protein markers will be performed using commercial enzyme-linked immunosorbent assay (ELISA) kits. Plasma metabolites will be measured with commercial enzymatic assay kits. All assays will be performed according to manufacturer's instructions and compliant to ISO13485 and cGMP.

Pockit diagnostics may sub-contract an external contract research organisation (CRO) to perform biomarker measurement. In this case, blood samples will be transferred from UMMC to the designated CRO.

Interim analyses may be performed upon collection of the first 100, or 200 samples. In all these cases, transfer of collected clinical data from the hospital site to Pockit diagnostics (or designated CRO) will be required to perform the interim analysis. Results from interim analyses will evaluate the necessity to modify the study protocol or to continue sample recruitment.

6. Study population

A total of up to 400 patients are expected to be recruited in this study. In order to be eligible for study participation, subjects must meet the following inclusion and exclusion criteria at the time of consent.

6.1. Inclusion criteria

- 1) Older than 18 years at time of consent;
- 2) Evaluated in the emergency department with suspected and code stroke activated.
- 3) Time from stroke onset < 18 hours

6.2. Exclusion criteria

- 1) Received thrombolytic therapy (e.g. tPA, Alteplase) before collection of blood;
- 2) (Anticipated) inability to provide a blood sample;
- 3) Time from stroke onset > 18 hours.
- 4) At time of consent participating in a Clinical Trial Investigational Medicinal Product (CTIMP)

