6.3. Withdrawal criteria

Patients and blood samples will be withdrawn from this study in case:

- 1) More than 60 minutes have passed from blood withdrawal to beginning of centrifugation;
- 2) Presence of haemolysis in blood plasma;
- 3) Absence of imaging results.

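### The plan lets an LVO patient's only blood sample be drawn after the imaging result is known, or after thrombectomy, and still count in the primary analysis

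*Combined protocol and SAP*

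**What the plan says.** All references are to the combined protocol and SAP.

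- **Intended use.** Sections 2 and 6.4 describe a rule-in test that identifies LVO before hospital, so that the patient can be routed to a thrombectomy centre. Section 2 names the treatment: "Acute ischaemic stroke patients with LVO can be effectively treated with endovascular thrombectomy".
- **Recruitment (5.1).** "Patients will be recruited as soon as possible after their arrival to ED and preferably before CT/MRI scans are performed". The same section adds: "Patients will be offered the possibility to take more time to consider participating".
- **Eligibility.** The opening of section 6 says that "subjects must meet the following inclusion and exclusion criteria at the time of consent". The onset limit in 6.1 is "Time from stroke onset < 18 hours".
- **Sample (5.2).** "One 5 mL sample of venous blood will be collected from each consented patient". No latest time for the draw is given.
- **Treatment exclusion (6.2).** "Received thrombolytic therapy (e.g. tPA, Alteplase) before collection of blood". Thrombectomy is not listed.
- **Withdrawal (6.3).** There are three grounds: "More than 60 minutes have passed from blood withdrawal to beginning of centrifugation", haemolysis, and missing imaging. None concerns the order of blood, imaging and treatment.
- **Reference standard (5.3).** LVO is diagnosed from CT angiography.
- **Data (7.1).** The interval from onset to blood collection is recorded. Times of imaging, of the imaging result and of thrombectomy are not listed.
- **Analysis (7.4).** Cases meeting 6.3 leave the primary analysis and are held for a separate sub-group analysis. No analysis considers whether blood came before or after imaging or thrombectomy.

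**The concern.** Exclusion 1 shows that the sponsor wants blood taken before reperfusion treatment. As written, it secures this for only one of the two treatments. Among LVO patients sampled late, it removes those given thrombolysis and keeps those who had thrombectomy alone.

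A sample drawn after thrombectomy reflects a patient whose occlusion has been treated, yet the recorded diagnosis is still LVO. Since thrombectomy is a treatment for LVO, these samples would fall essentially in one diagnostic group. They would bear on sensitivity and LR-, both primary outcomes in 4.1, and on the share of LR+ and accuracy that depends on sensitivity.

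Enrolment once the scan result is known is a milder form of the same problem. The patient studied is then no longer the un-imaged patient for whom the test is intended.

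There is also a knock-on effect. The kinetics analysis in 7.4 bins patients by onset-to-blood time and will inform whether the test is limited to a time window. If later bins hold more post-thrombectomy samples, elapsed time and treatment are mixed.

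**Working it through.** **Step 1: does any rule stop a late sample?** Take an LVO patient evaluated in the ED under a code stroke and approached there, who consents late or is sampled late.

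| Rule | Stops blood after the imaging result? | Stops blood after thrombectomy without thrombolysis? |
|---|---|---|
| 5.1, recruit promptly, ideally before the scan | No, a preference | No |
| 6.1, under 18 hours from onset, judged at consent | No | No, if consent falls inside the window |
| 6.2, exclusion 1 | No | No, thrombolysis only |
| 6.3, withdrawal | No | No |
| 7.4, analysis | No restriction | No restriction |

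The sample enters the primary analysis. With one sample per patient, no earlier one can replace it.

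**Step 2: which part of the test is exposed?** FAST-ED and FAST are scored by ambulance paramedics, and other scales are collected pre-hospitally (7.1), so they precede treatment at the recruiting site. Only D-dimer and GFAP can be altered by a late draw.

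**Step 3: the plan's own figure.** Section 6.4 gives 329 patients at 20% prevalence: 0.20 × 329 = 65.8, so 66 LVO cases, as stated. (The 329 itself reproduces with an exact binomial test at one-sided 5%: 263 non-LVO patients, 263/0.80 = 328.75, rounded up to 329. With the stated two-tailed 5% the same method gives 316/0.80 = 395. That is a separate matter; only the 66 is used here.)

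**Step 4: scale per case.** 1/66 = 0.015, so each changed result moves sensitivity by about 1.5 points.

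**Step 5: illustration.** The documents give neither the share of LVO cases sampled late (f) nor their detection rate (Se_late). Both are assumed, as is the pre-treatment sensitivity (Se_pre).

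Se_obs = (1 − f) × Se_pre + f × Se_late

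| Se_pre | f (cases of 66) | Se_late | Se_obs |
|---|---|---|---|
| 80% | 10% (6.6) | 50% | 77.0% |
| 80% | 10% (6.6) | 95% | 81.5% |
| 80% | 20% (13.2) | 50% | 74.0% |
| 80% | 20% (13.2) | 95% | 83.0% |
| 70% | 10% (6.6) | 30% | 66.0% |
| 70% | 10% (6.6) | 90% | 72.0% |
| 70% | 30% (19.8) | 30% | 58.0% |
| 70% | 30% (19.8) | 90% | 76.0% |

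LR- = (1 − sensitivity)/specificity. At the target specificity of 95%, sensitivity of 80% gives 0.20/0.95 = 0.21, 74% gives 0.26/0.95 = 0.27, and 83% gives 0.17/0.95 = 0.18.

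**Step 6: comparison with sampling error and the floor.** At 80% and 66 cases the standard error is √(0.80 × 0.20/66) = 4.9 points, so a 95% interval is about ±10 points. Section 7.4 refines the model if sensitivity is below 60%. Since 0.60 × 66 = 39.6, that means 39 or fewer detected. From 46/66 (69.7%) this takes a net 46 − 39 = 7 lost detections; from 53/66 (80.3%) it takes 53 − 39 = 14.

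**The case against.** The strongest reply is that 5.1 already describes the right workflow: recruitment at ED arrival, without delay, with the approach made during the ED visit, and a consent waiver for patients who cannot consent. A site following that workflow would rarely sample after thrombectomy. The study is powered on specificity, which post-thrombectomy samples hardly touch. Laboratory staff are blinded (7.2), the thresholds are fixed in advance, and most shifts in the illustration lie inside the sampling error.

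Much of this stands, and it limits the point. It makes late sampling less likely but does not prevent it. Sampling error does not excuse a bias either: the interval would be centred on the wrong value, and a larger sample would not correct it.

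A reader might infer more than the documents support:

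- **That sites will first approach patients after thrombectomy, or enrol transfers with a known LVO.** A first approach after the procedure departs from 5.1. Section 2 mentions transfers as general background; nothing says that the study sites receive them. The stroke-unit wording in the abstract does not override the ED requirement in 6.1. The gap is delayed consent or a delayed draw.
- **That LVO cases are chosen on the scan result.** Prevalence monitoring in 6.4 only adjusts sample size outside a 10-30% band; it is not a rule for choosing patients. Recruiters are not said to be blind to imaging, but that does not show selection.
- **That affected patients could never be found.** The times should be in hospital records, and long onset-to-blood intervals would hint at late draws. What is true is that the times are not listed study data.

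**Conclusion.** The point holds as a statement of what the text permits, not of what will happen. Recruitment before imaging is preferred rather than required, the draw has no deadline, and thrombectomy is missing from both sets of criteria. A sample drawn after the imaging result, or after thrombectomy without thrombolysis, can therefore enter the primary analysis as an LVO case.

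The firm figure is about 1.5 points of sensitivity per changed result, given the planned 66 LVO cases. Everything beyond that rests on assumed values. Under them, observed sensitivity ranges from 74% to 83% around a pre-treatment 80%, and from 58% to 76% around 70%. Only the most adverse of these cases crosses the 60% floor. The documents do not say how thrombectomy changes D-dimer or GFAP, so the direction is unknown.

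This is a cheap improvement worth making. It is not evidence that the study's estimates are biased.

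**What to change.** 1. Extend exclusion 1 in 6.2 so that the sample-eligibility rule also covers blood collected after the start of endovascular thrombectomy, and add the same rule to 6.3. Both places are needed: section 6 judges eligibility at consent, and 6.3 catches a procedure that starts between consent and the draw. Such samples then go to the separate sub-group analysis already provided for in 7.4. This governs samples and the analysis set only; it changes nothing in patient care.
2. Add to 7.1 the clock times of the blood draw, the first CT/CT angiography, availability of the CT angiography result and the start of thrombectomy, and whether the patient arrived with prior vascular imaging.
3. Add to 7.4 a repeat of the primary accuracy estimates in patients whose blood was drawn before the CT angiography result was available, reported beside the full-cohort estimates.

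The cost is protocol wording, a few CRF fields that should be available from hospital records, and one more run of a planned analysis. A few LVO cases may leave the primary set, which slightly widens the interval for sensitivity. Item 3 shows whether the estimates depend on timing; it does not by itself show how patients came to be enrolled. If no patient is affected, the recorded times let the sponsor demonstrate it.

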6.3. Withdrawal criteria

Patients and blood samples will be withdrawn from this study in case:

- 1) More than 60 minutes have passed from blood withdrawal to beginning of centrifugation;
- 2) Presence of haemolysis in blood plasma;
- 3) Absence of imaging results.

6.4. Sample size estimation

The proposed intended use of the test is to rule in patients with LVO to redirect them to EVT-capable centers from a population of suspected stroke, thus we powered the study on specificity. Assuming a prevalence of 20%, a minimum specificity of 90%, a two-tailed 5% type I error rate (**a**) and 90% power (**β**), a sample size of 329 suspected stroke patients with 66 LVO cases would detect a diagnostic specificity of 95% (95%CI: 90%–100%) for each

algorithm. Accounting for 20% of data loss due to missing patient data or sample lysis, a final number of 395 patients will be required.

Sample size estimation was performed according to Chu and Cole⁸.

Prevalence of LVO/ischemic stroke will be monitored during recruitment to ensure that calculated sample size is appropriate for actual prevalence. A prevalence in the range of 10-30% LVO will be accepted. In case observed prevalence will be outside the acceptable range, sample size will be re-estimated and recruitment size adjusted accordingly.

7. Data management

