7.4. Data analysis plan

Clinical and biomarker data will be curated after clinical and technical monitoring to assure maximum validity of the data utilised to construct the algorithm. Any subject matching

criteria as defined in section "6.3 – Withdrawal criteria" will not be incorporated into the primary analysis. This data is quarantined for a separate sub-group analysis where relevant.

Data exploration

Data will be explored by generating box plots of blood biomarker concentrations (plasma or whole blood) and clinical data, according to stroke subtypes. Concentrations of blood biomarkers and clinical data (where applicable) may undergo pre-processing and/or transformations to ensure statistical assumptions are met prior to analysis. Akaike information criterion (AIC) will be used to assess the need of transformations.

Whole blood biomarker concentrations

Plasma concentration of individual biomarkers will be adjusted based on whole bloodto-plasma (WBP) ratios, in order to obtain whole blood biomarker concentrations. Values of biomarker concentrations (plasma or whole blood) will be reported with corresponding values of standard error of the mean (s.e.m.).

Covariate analysis

Association between clinical variables and concentration of individual blood biomarkers will be assessed. A linear regression model between biomarker concentration (as the outcome) and key clinical covariates will be generated.

Biomarker kinetics

To assess the effect of biomarker kinetics on diagnostic performance, patient population will be divided into 3-hour and 6-hour bins based on their stroke onset to blood collection time and multivariate logistic regression will be performed on each population bin separately. Alternatively, the distribution of stroke onset to blood collection times will be assessed and the population will be divided into quartiles or halves, and compared. Results from this analysis will be compared to results obtained on the whole population and will inform if the test will be limited to a specific time window from stroke onset.

Diagnostic performance

Values of diagnostic accuracy, sensitivity, specificity, positive and negative likelihood ratios will be calculated and reported with confidence intervals. ROC curve will be drawn and the area under the ROC curve will be reported with confidence intervals. Confidence intervals will be estimated via 2000 bootstrapped replicates.

Biomarker diagnostic thresholds

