Thresholds of individual biomarkers already established by Pockit diagnostics will be validated for their diagnostic performance. If the accuracy achieved by the model is below acceptable levels (specificity <90% and/or sensitivity<60%) we will aim to refine the model using data from our 395 patient cohort.

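### Section 6.4 claims 90% power at a two-tailed 5% level, but 263 non-LVO patients give 83.0% with an exact or Wilson limit and 88.8% with mid-p or Jeffreys

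*Combined protocol and SAP*

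**What the plan says.** Section 6.4 (Sample size estimation) powers the study on specificity. It gives the design inputs as "Assuming a prevalence of 20%, a minimum specificity of 90%, a two-tailed 5% type I error rate", adds 90% power, and concludes that "a sample size of 329 suspected stroke patients with 66 LVO cases would detect a diagnostic specificity of 95" per cent, for each algorithm, with a 95% CI written as 90% to 100%. The method is referenced to a paper on exact sample-size methods for diagnostic tests. A 20% allowance for data loss takes 329 to 395. The section also says "A prevalence in the range of 10-30% LVO will be accepted" without re-estimation. Section 6 caps the study: "A total of up to 400 patients are expected to be recruited in this study".

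The test or interval that would show specificity above 90% is not named. Section 7.4 (Diagnostic performance) says only that "Confidence intervals will be estimated via 2000 bootstrapped replicates". It gives no bootstrap type and no confidence level.

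**The concern.** Error rate, power, null value, target value and sample size are all stated, so the claim can be checked. Specificity is estimated in non-LVO patients only, so the relevant sample is 263, not 329. That number looked too small for 90% power with 2.5% in the upper tail.

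Specificity is the quantity the study was sized on, and it is a primary outcome. A reader would expect a truly 95%-specific algorithm to miss the 90% bar one time in ten. If the miss rate is higher, or 90% power is bought with a larger false-positive rate, then the design statement is wrong and the reported specificity interval will be misread.

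**Working it through.** **Inputs (Section 6.4).** Null specificity p0 = 0.90; target p1 = 0.95; two-tailed 5%, taken as 2.5% in the upper tail (the usual convention, which the plan does not spell out); power 90%; prevalence 20%; non-LVO patients n = 329 − 66 = 263.

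**Reproducing 329.** For each n, take the smallest cut-off c with P(X ≥ c | n, 0.90) no larger than the allowed tail, then power = P(X ≥ c | n, 0.95). Exact binomial power moves in a saw-tooth as n rises, so two values of n are shown.

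| Upper tail | Power first reaches 90% at n | Power stays ≥ 90% from n | Total = n/0.8 (stable) |
|---|---|---|---|
| 5% (one-sided 5%) | 239 | 263 | 328.75, i.e. 329 |
| 2.5% (two-tailed 5%) | 292 | 316 | 395 |

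The plan's 329 is reproduced exactly under a one-sided 5% exact test, and not under the two-tailed level it states. The 395 in the last row is an evaluable number. It equals the plan's recruitment target by coincidence, since that target is 329 × 1.2 = 394.8.

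**Power at n = 263.**

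| Cut-off c | P(X ≥ c), p = 0.90 | P(X ≥ c), p = 0.95 |
|---|---|---|
| 244 | 7.65% | 95.7% |
| 245 | 4.90% | 92.9% |
| 246 | 2.97% | 88.8% |
| 247 | 1.71% | 83.0% |

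The cut-off each method implies, from its 95% lower limit:
- Exact (Clopper-Pearson): 0.8985 at 246 and 0.9031 at 247, so 247.
- Wilson: 0.8989 at 246 and 0.9035 at 247, so 247.
- Jeffreys: 0.8963 at 245 and 0.9008 at 246, so 246. Mid-p: one-sided p 0.0394 at 245 and 0.0234 at 246, so 246.
- Two-sided exact test summing all outcomes no more likely than the one observed, which does not assume equal tails: p = 0.099 at 245, 0.063 at 246 and 0.031 at 247, so 247.

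**Percentile bootstrap.** With 2000 replicates and 4000 simulated runs per count, the 95% lower limit reaches 0.90 in 0% of runs at 244 and in about 100% at 246. At 245 it does so in 66% of runs (resampling the 263 non-LVO patients) or 36% (resampling all 329). Hence:
- error: 0.66 × 4.90% + 0.34 × 2.97% = 4.2%, or 0.36 × 4.90% + 0.64 × 2.97% = 3.7%;
- power: 0.66 × 92.9% + 0.34 × 88.8% = 91.5%, or 0.36 × 92.9% + 0.64 × 88.8% = 90.3%.

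The idealised limit, resampling within the 263, has cut-off 245: power 92.9%, error 4.9%.

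**Random non-LVO count.** Average power over a non-LVO count distributed Binomial(N, 1 − prevalence), for 329 evaluable and for 316 (395 less 20%):

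| Prevalence | Exact, 2.5% tail: 329 / 316 | Exact, 5% tail: 329 / 316 |
|---|---|---|
| 10% | 88.5% / 87.0% | 94.1% / 93.2% |
| 20% | 84.2% / 82.4% | 91.1% / 90.0% |
| 30% | 77.8% / 76.0% | 87.1% / 85.8% |

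At 20% prevalence the Wilson averages are 84.7% / 83.0%. At 329, mid-p gives 86.7% and Jeffreys 87.1%. A fixed 253 non-LVO (316 × 0.8 = 252.8) gives 79.9% with the exact 95% limit.

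**The printed interval.** The exact 95% interval for 250/263 is 91.7% to 97.3%, not 90% to 100%.

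**The case against.** The best reply is that Section 7.4 plans a bootstrap, not an exact or Wilson limit, and that a 95% percentile bootstrap does reach 90% power. That is true of the power, but the error rate then departs from nominal: the upper tail is 3.7–4.9% instead of 2.5%. A Wald interval has the same cut-off of 245 and fails the same way, with total error 6.3%. A BCa bootstrap resampled within non-LVO patients moves the cut-off to 246, which is back to 88.8%.

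Second, both stated figures can literally be met by an unequal split: rejecting at 245 or more, or at 220 or fewer, has total error 4.99% and power 92.9%. This stands as a technical point. It puts 4.90% in the favourable tail, and the plan states no such rule.

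Third, 88.8% is close to 90%. That is fair. The weight rests on the 7-point gap with the exact limit, which is the family of methods Section 6.4 cites.

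Fourth, no trial decision turns on this. The refinement trigger in Section 7.4, "If the accuracy achieved by the model is below acceptable levels (specificity <90% and/or sensitivity<60" per cent), names no confidence limit and is unaffected. That limits the consequence to a misdescribed design property and a misread interval. Finally, power rises at low prevalence, but even at 10% the averaged exact two-tailed figure stays below 90%.

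**Conclusion.** The concern holds. As written, 329 evaluable patients do not give 90% power at an equal-tailed two-tailed 5% level for specificity of 95% against 90%. With an exact or Wilson interval, a truly 95%-specific algorithm fails to exclude 90% about 15–17% of the time; with mid-p or Jeffreys, about 11–13%. With a 2000-replicate percentile bootstrap, an algorithm at exactly 90% appears to exceed 90% about 1.5–1.7 times as often as a nominal 2.5% (3.7/2.5 to 4.2/2.5).

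These figures assume 20% prevalence, 2.5% in the upper tail and, for the bootstrap, a 95% percentile interval. That 329 came from a one-sided 5% calculation is inference; the mismatch does not depend on it. The printed 95% CI is a secondary labelling point, since it may be meant as a target range. This should be fixed, but it does not invalidate the study.

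**What to change.** Choose one of three.

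- **(a) One-sided 5%.** Restate the error rate in Section 6.4 as one-sided 5%, and in Section 7.4 report specificity with a two-sided 90% exact or score interval in place of the bootstrap. Both have cut-off 245 at n = 263 (lower limits 0.9002 and 0.9013). Exact power is then about 91% at 329 evaluable and 90% at 316, at 20% prevalence. State the values over the accepted range: about 93–94% at 10% and 86–87% at 30%. The cost is a weaker stated error standard.
- **(b) Two-tailed 5%.** Keep the level, report specificity with a 95% exact or score interval in Section 7.4, and restate power in Section 6.4 as about 83–85% at 329 evaluable (about 80–83% at 316). The cost is a less favourable stated power.
- **(c) Both targets.** Raise the sample to 292 non-LVO (first crossing) or 316 (stable), that is 365 to 395 evaluable. With the plan's own multiplier this is 365 × 1.2 = 438 to 395 × 1.2 = 474 recruits, 43 to 79 more than 395 and above the ceiling of 400 in Section 6.

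Options (a) and (b) need only new wording in Section 6.4 and one sentence in Section 7.4, with no extra patients, so either is the cheaper repair. In every case, label the 90% to 100% range as a target, or replace it with the expected exact interval (about 91.7% to 97.3% at 263 non-LVO; recompute it under (c)).
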